Research Proposal
[name], DO
WSU-SOM, OBGYN, PGY-2

Title

- Postpartum management of gestational hypertensive disorders using furosemide: A randomized controlled trial

Investigators

- Primary Investigator
 - [name], DO, PGY-2, Capt, USAF
 - [contact]
 - [contact]
- Investigators
 - [name], MFM subspecialist at MFMUG
 - [contact]
 - [contact]
 - [name], WSU-SOM Teaching Faculty
 - [contact]
 - [contact]

Summary

- The main purpose of this study is to learn if incorporating a loop diuretic such as furosemide along with labetalol in the routine management of postpartum gestational hypertensive disorders could lower the need for additional anti-hypertensive agents to control blood pressures, improve blood pressures (as measured by systolic blood pressure, diastolic blood pressure and mean arterial blood pressures), shorten hospital stays and decrease readmissions for patients with gestational hypertensive disorders.
- Based on a study by Veena et al¹, there is reason to believe that the addition of furosemide to other anti-hypertensives may help decrease the need to add or increase the dose of medication to control blood pressures. There may be potential to shorten hospital stays and decrease readmissions, as well. Collecting data will be done using a prospective, randomized 1:1 controlled study assigning postpartum patients with a gestational hypertensive diagnosis to either labetalol alone or labetalol plus furosemide.
- Based on an estimated 8% need for increase in anti-hypertensive medication in the furosemide group and a 26% need in the standard treatment arm, to achieve 90% power

with a 2-sided alpha of 0.05, we calculate 96 patients per group. Analysis will be via Chi-square or Fisher's exact test for categorical variables. Student T-Test and Mann Whitney U tests will be utilized to compare continuous variables. Randomization will be performed using REDCap.

- The study will be performed in the postpartum wing of Miami Valley Hospital Main Campus and would recruit patients who have consented to participate in the study with enrollees coming from the OB Staff population.

Background and Literature Review

- We found four studies investigating loop diuretics in the management of postpartum hypertensive disorders- Matthews et al², Ascarelli et al³, Amorim et al⁴, and Veena et al. Of these studies, only Amorim and Veena were able to show statistical significance on any parameters. Amorim was able to show that there was an improvement of SBP, DBP and MAP, but their research was only presented as an abstract at a conference and not published, thereby making it impossible to draw any conclusions or practice guidelines. Veena demonstrated that by using furosemide and nifedipine in combination, the need for additional antihypertensive medication in severe pre-eclampsia in the postpartum period was reduced when compared to nifedipine alone.
- A systematic review⁵ of postpartum hypertensive disorder management suggested that there was insufficient data to recommend any single pharmacological intervention at this time in the management of gestational hypertensive disorders. The review emphasized the need for further studies to be conducted to help guide management of patients affected by gestational hypertensive disorders in the future.

Objectives

- **Main Question**
 - Does the use of furosemide plus labetalol improve blood pressures in the postpartum period of patients with gestational hypertensive disorders versus labetalol alone?
 - **Primary**
 - Does the addition of a 5-day course of furosemide to labetalol avoid the escalation of anti-hypertensive therapy to control blood pressures.
 - **Secondary:**
 - Does the addition of furosemide to labetalol in postpartum hypertension:
 - Improve of systolic blood pressure, diastolic blood pressure and mean arterial pressure.
 - Shortened hospital stay
 - Affect breastfeeding status at 1 week postpartum visit in mothers planning to breastfeed.
 - Decrease readmission for postpartum hypertensive disorders.

Significance to patient, institution, and profession

- As a busy referral center with a level 3 NICU, Miami Valley care for a large number of patients with gestational hypertensive disorders
- The majority of the OB staff population being served at Miami Valley Hospital is African American. According to Myatt⁶, the incidence of pre-eclampsia in the African American population is greater than double the Caucasian population (11% to 5%) thereby making this study very applicable to our patient population.
- With the construct of the study, we would be keeping costs low by utilizing already established resources and practices (blood pressure cuffs, nurses, routine one week blood pressure checks) while only adding on the unit cost of furosemide and basic metabolic panels.
- If treatment with labetalol and furosemide is found to be useful, it would be not only a very inexpensive, cost effective way of improving patient outcomes and possibly decreasing lengths of stay, but possibly improvement in global practice in places that are lacking in resources privy to first world countries.

Methods

- A prospective randomized 1:1 controlled trial including postpartum women with gestational hypertension or preeclampsia
 - Inclusion criteria: Age 18-45, Postpartum: 24-72 hours after delivery, no contraindications to the study medications
 - Exclusion criteria: chronic hypertension diagnosis, creatinine levels above 1.5 $\mu\text{m}/\text{L}$, unable to give consent
- One arm receiving 200mg labetalol BID alone on Day#1 or at least 24 hours after magnesium sulfate, if given
- One arm receiving 200mg labetalol BID and a five day course of furosemide 20mg QD on Day#1 or 24 hours after magnesium sulfate
 - The 20 mg dose is the standard dose for furosemide in this population.
- Titrate labetalol to maintain blood pressures below 150 SBP and/or 100 DBP per ACOG recommendations.⁷
 - In the event of persistently elevated blood pressures, labetalol will be increased to 400mg BID and escalated to 600mg BID and finally 800mg BID as indicated
- Measurement of blood pressure every four hours until patient discharge
- Daily BMPs to assess for electrolyte abnormalities
- Measurement of urine output every 12 hours until discharge
- Demographics
 - Age (18-24, 25-34, 35-44, 45-51)
 - Nulliparous (yes, no)
 - BMI (underweight, normal, overweight, obese)

- Race (Caucasian, African American, Asian, Hispanic, Other)
- Diabetes (yes, no)
- Multiple gestation (yes, no)
- Preterm delivery (yes, no)
 - Gestational age at delivery
- Cesarean delivery (yes, no)
- IVF pregnancy (yes, no)
- History of previous gestational hypertension/pre-eclampsia (yes, no)
- Systemic lupus erythematosus (yes, no)
- Renal disease (yes, no)
- Outcome variables
 - Need for additional antihypertensive medication (yes, no)
 - Labetalol 400mg BID
 - Labetalol 600mg BID
 - Labetalol 800mg BID
 - Highest systolic blood pressure (mmHg)
 - Highest diastolic blood pressure (mmHg)
 - Mean arterial blood pressure
 - Daily urine output (mL)
 - Length of postpartum stay (days)
 - Readmission for hypertension (yes, no)
 - Breastfeeding at 1 week postpartum (yes, no)
- The study duration is the length of the hospital stay plus 1 week postpartum blood pressure check.
- The research will be analyzed and interpreted by the research team conducting the study.
- Potential difficulties and limitations include compliance concerns of mandatory one week blood pressure follow up appointment.
- The unit cost of one tablet of labetalol 200mg and furosemide 40mg is currently \$0.32 and \$1.23, respectively.^{8,9}
- The study would use already readily available automated blood pressure cuff machines on the postpartum wing.

Safety Monitoring

Monitoring of blood pressures will be performed every four hours while on the maternity postpartum floor. If the patient is found to be above 160 systolic or 110 diastolic, it will be rechecked in fifteen minutes. If still elevated, then escalation of blood pressure medicine will be done. The healthcare provider will ask the patient if they are exhibiting any signs of profound hypertension and/or hypokalemia including headache, vision changes, dizziness, lightheadedness, weakness, fatigue, muscle cramping, or heart palpitations. If any of these are identified, a physician will be notified and will assess the patient.

Patients will be instructed to let their doctor/nurses know if they are experiencing known side effects of Lasix that include new onset weakness, fatigue, muscle cramping, dizziness or

heart palpitations. If a patient has severe symptoms after discharge, they will be instructed to call the afterhours phone number on the consent form.

If a patient has signs of hypokalemia, we will test lab values for potassium (K+) levels (Complete metabolic panel). We will continue administering Lasix if the potassium result is between 3.0 and 3.4 $\mu\text{m}/\text{L}$ and we will administer 20 mEq KDur BID. If it is less than 3.0 $\mu\text{m}/\text{L}$ we will stop using Lasix.

References

- 1) Veena, P., et al. “Furosemide in Postpartum Management of Severe Preeclampsia: A Randomized Controlled Trial.” *Hypertension in Pregnancy*, vol. 36, no. 1, 2016, pp. 84–89., doi:10.1080/10641955.2016.1239735.

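### The current diagnosis and its severity are not recorded, stratified on or used in the primary test, and the 90% power holds only at 26% and 8%, rates given without a source

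*Protocol*

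**What the plan says.** - **Population.** Protocol, Methods: "A prospective randomized 1:1 controlled trial including postpartum women with gestational hypertension or preeclampsia". The inclusion line adds age, a window of 24 to 72 hours after delivery, and no contraindication. It sets no severity level, no blood pressure level and no treatment indication.
- **Variables.** The demographics list in Methods covers a history of these disorders in an earlier pregnancy. Neither it nor the outcome list has a field for the current qualifying diagnosis or its severity.
- **Allocation.** The Summary says that REDCap will be used, 1:1, and names no strata.
- **Primary analysis.** The SAP compares the arms by Fisher's exact test on the number of women with any labetalol increase in hospital, without covariates or strata.
- **Evidence.** Background and Literature Review reports one result on this endpoint, from a trial of furosemide added to nifedipine: "the need for additional antihypertensive medication in severe pre-eclampsia in the postpartum period was reduced when compared to nifedipine alone".
- **Sample size.** Summary: "Based on an estimated 8% need for increase in anti-hypertensive medication in the furosemide group and a 26% need in the standard treatment arm". For 90% power, "with a 2-sided alpha of 0.05, we calculate 96 patients per group". The rates are called estimates and no source is attached to them.

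**The concern.** The primary event is a response to blood pressure after delivery, so severity of the qualifying disorder plausibly predicts it. The trial admits the whole range of severity but keeps no record of where each woman falls in it. Three things follow.

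1. A reader cannot tell how the enrolled women compare with those in the supporting trial. After a null result it would be hard to separate an ineffective drug from a population with few events.
2. Balance between arms on diagnosis cannot be shown, and the primary test cannot use diagnosis even if it predicts the outcome strongly.
3. The 90% power is stated without qualification, although it rests on a control rate whose origin and fit to this population are not explained.

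**Working it through.** **Inputs.** 26% and 8%, two-sided alpha 0.05, 90% power, 96 per group (Protocol, Summary); Fisher's exact test (SAP, Primary). Implied relative risk: 0.08 / 0.26 = 0.308.

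**Step 1: reproduce the plan's figure.** Exact power is the sum, over all x and y from 0 to n, of Bin(x; n, p1) × Bin(y; n, p2), counting only tables with a two-sided Fisher p-value of at most 0.05. At p1 = 0.26 and p2 = 0.08:

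- n = 95: 89.95%
- n = 96: 90.3%

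So 96 is the size at which exact Fisher power passes 90%. The figure reproduces, with almost no reserve.

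**Step 2: vary the control rate at the same relative risk.** The treated rate is 0.308 × the control rate, with n = 96 per group. For control rates below 26%, f = 1 − (control rate / 0.26). This can be read as the share of women with essentially no chance of an event. The documents do not give f.

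| Control | Furosemide | f | Exact Fisher power |
|---|---|---|---|
| 30% | 9.2% | – | 95% |
| 26% | 8% | 0 | 90% |
| 23.4% | 7.2% | 10% | 86% |
| 20.8% | 6.4% | 20% | 80% |
| 18.2% | 5.6% | 30% | 72% |
| 15.6% | 4.8% | 40% | 63% |
| 13% | 4% | 50% | 53% |

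Zero risk is the harshest reading. If the low-risk women have a 5% control rate instead, the overall control rate is 0.26(1 − s) + 0.05s for a low-risk share s. At s = 25% this is 20.75% and power is 80%. At s = 50% it is 15.5% and power is 63%.

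**Step 3: what a stratified test would do.** Assumptions, none from the documents: 40% of women have severe disease (38 of 96 per arm, equal by stratified allocation), relative risk 0.308 in both strata, and an overall control rate of 26%. If the severe stratum has r times the control rate of the rest, the rest have 0.26 / (0.4r + 0.6). The Mantel-Haenszel statistic is [Σ(a − n1·m/t)]² / Σ[n1·n0·m(t − m) / (t²(t − 1))], where a stratum has a events among n1 treated women, n0 controls, m events in all and t women. It is used without continuity correction and compared with 3.84. Each line below comes from 200,000 simulated trials. Type I error uses the control rates in both arms.

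| r | Control rate, severe / rest | Power: stratified | Power: pooled Fisher | Type I: stratified | Type I: pooled Fisher |
|---|---|---|---|---|---|
| 1 | 26% / 26% | 93.0% | 90.2% | 5.1% | 3.6% |
| 2 | 37.1% / 18.6% | 93.6% | 90.7% | 5.0% | 3.1% |
| 4 | 47.3% / 11.8% | 94.9% | 91.2% | 5.0% | 2.2% |
| 8 | 54.7% / 6.8% | 96.5% | 92.3% | 5.1% | 1.2% |

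At r = 1 severity carries no information, so that gain of about 3 points is only the removal of Fisher's conservatism. With a continuity correction, a rough stand-in for the exact stratified test, power is 89.5%, 90.6%, 92.3% and 94.3%. That is no gain at r = 1 or 2, and 1 to 2 points at r = 4 or 8.

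**The case against.** **A broad population is a legitimate choice.** The title, Summary and main question all concern gestational hypertensive disorders, and eligibility matches them. A reader might infer that eligibility contradicts the objective, because the stem of the secondary objectives reads "Does the addition of furosemide to labetalol in postpartum hypertension". The documents do not support that reading: the primary objective carries no such restriction, and one loosely worded secondary stem does not redefine the trial. This objection stands.

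**Dilution is not shown.** A reader might also infer that the control rate must fall below 26%. The documents give no case mix and no event rate by severity. The event here is any labetalol increase, on a different background drug from the supporting trial, so the rate could move either way. The trigger for an increase is itself unsettled: Methods titrates to below 150/100, while Safety Monitoring acts above 160/110. Those passages must be reconciled, because the trigger helps set the event rate. This objection also stands, so Step 2 shows sensitivity and does not forecast.

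**The origin of 26% and 8% is inferred.** The Summary names the severe pre-eclampsia trial just before giving the rates, but does not say they come from it. The fair request is to state the source.

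**The pooled Fisher test is valid.** Chance imbalance is already allowed for in its error rate, and the SAP's Day 0 blood pressures will show part of any difference in severity. That stands too. What it leaves is that diagnosis remains unrecorded, at very little saving.

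**Conclusion.** The point holds as a cheap improvement and a matter of disclosure. It is not an error that invalidates the trial.

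Three things are plain from the documents: severity is unrestricted at entry, the current diagnosis and its severity are not among the listed variables, and neither the allocation nor the primary test uses them. The sample size calculation is correct at its own inputs. The stated 90% should be read as power at 26% versus 8% only, because 96 per group has no margin. Under a constant relative risk, a control rate of 20.8% would give 80% and one of 13% would give 53%. A rate above 26% would give more than 90%. Which applies cannot be settled from the documents.

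Under the assumptions of Step 3, the uncorrected stratified test has about 93% to 96% power against 90% to 92% for pooled Fisher, and holds its type I error near 5%. Part of that gain comes from leaving Fisher's conservatism behind. The part owed to severity depends on how strongly it predicts escalation. The gain in interpretability, from knowing who was enrolled, does not depend on those assumptions.

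**What to change.** 1. **Record** the qualifying diagnosis before randomisation, in three levels: gestational hypertension, preeclampsia, preeclampsia with severe features.
2. **Stratify** the REDCap allocation by it, with a rule fixed in advance for merging sparse levels.
3. **Analyse** the primary endpoint with a Cochran-Mantel-Haenszel test over these strata, or its exact version. The SAP should say which, and keep the pooled Fisher test as a sensitivity analysis. Report event counts by stratum and arm descriptively.
4. **State** the source of 26% and 8%, describe the 90% as conditional on them, and give power over a range of control rates. The sample size stays at 96 per group.
5. **Clarify** whether entry also requires current hypertension or an indication for treatment. That is for the investigators to decide: a narrower entry rule might raise the event rate but would slow recruitment and limit applicability.

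The cost is one baseline field, a stratified list, a small SAP change and a few sentences in the Summary. Two drawbacks should be accepted openly: the stated power will look less secure, and the exact stratified test may gain little if severity turns out to predict escalation only weakly.

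### Between 150/100 and 160/110 the primary event depends on an undefined judgement of persistent elevation, with no masking described

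*Protocol*

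**What the plan says.** The SAP (Primary, analysis plan) compares the arms by Fisher's exact test on the number of women with any increase in labetalol dose during the hospital stay. The event is therefore a treatment decision rather than a measurement.

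Protocol, Methods, governs that decision in two lines:

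- The target: "Titrate labetalol to maintain blood pressures below 150 SBP and/or 100 DBP per ACOG recommendations".
- The steps: "In the event of persistently elevated blood pressures, labetalol will be increased to 400mg BID and escalated to 600mg BID", with the ladder ending "escalated to 600mg BID and finally 800mg BID as indicated".

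Protocol, Safety Monitoring, adds a rule at a higher level: "If the patient is found to be above 160 systolic or 110 diastolic, it will be rechecked in fifteen minutes". It continues: "If still elevated, then escalation of blood pressure medicine will be done".

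The comparator is described as "One arm receiving 200mg labetalol BID alone on Day#1". Neither document mentions a placebo, masking or independent adjudication. Readings follow a fixed schedule in both arms: "Measurement of blood pressure every four hours until patient discharge".

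On blood pressure itself, the Protocol lists highest systolic, highest diastolic and mean arterial pressure as outcome variables. The SAP (Secondary 1) plans repeated measures ANOVA on daily means at baseline, Day 1 and Day 2.

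**The concern.** Because any increase counts, the first step from 200 mg to 400 mg BID settles a woman's event status. Above 160/110 that step follows from a confirmed reading. Between 150/100 and 160/110 it follows from someone's view that pressures have stayed high. The documents give no count of readings, no interval and no averaging rule. The 'and/or' in the target also leaves open whether one or both limits must be exceeded.

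With no masking described, the person making that call may know who is receiving furosemide. If women in this band are handled materially differently by arm, the primary comparison contains a difference that is not a drug effect.

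The planned blood-pressure analyses would give only indirect evidence of this. An arm with fewer escalations but no lower pressures would be a hint. But titration itself changes the pressures, and no planned analysis links a woman's readings to her own dose change. The plan as written could not show whether individual escalations followed the readings.

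**Working it through.** **1. Where the rule is and is not defined**

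| Pressure | Rule in the documents | Event status decided by |
|---|---|---|
| Above 160 systolic or 110 diastolic | Recheck at 15 minutes, escalate if still elevated (Safety Monitoring) | Readings |
| From 150/100 up to 160/110 | Increase if persistently elevated (Methods) | Judgement |

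**2. The plan's own figure**

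Inputs (Protocol, Summary): 26% against 8%, two-sided alpha 0.05, 90% power, 96 per group. Test (SAP, Primary): Fisher's exact.

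The rejection probability by full enumeration is

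P(reject) = Σₐ Σ_b Bin(a; 96, p_C) · Bin(b; 96, p_F) · 1[two-sided Fisher p(a, b) ≤ 0.05],

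where C is control and F is furosemide. With p_C = 0.26 and p_F = 0.08, power is 0.903 at 96 per group and 0.8995 at 95. So 96 reproduces as the smallest number reaching 90%.

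**3. Effect of arm-dependent handling when the drug does nothing**

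The documents give no size for any bias, so the shifts below are assumptions. Furosemide has no effect, p_C = 0.26, and handling alone lowers p_F.

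| Shift in furosemide arm | p_F | Women (shift × 96) | Total rejection | Of which false benefit |
|---|---|---|---|---|
| 0 | 0.26 | 0 | 0.0349 | 0.0174 |
| 3 points | 0.23 | 2.9 | 0.0565 | 0.0517 |
| 5 points | 0.21 | 4.8 | 0.0991 | 0.0974 |
| 8 points | 0.18 | 7.7 | 0.2189 | 0.2186 |

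**4. How much differential handling those shifts require**

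Only escalations inside the band are discretionary. Let s be the share of escalations in the band. The fraction w of them that must be withheld in the furosemide arm alone is w = shift / (0.26 × s).

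| s (assumed) | 3 points | 5 points | 8 points |
|---|---|---|---|
| 0.25 | 46% | 77% | 123% (impossible) |
| 0.50 | 23% | 38% | 62% |
| 0.75 | 15% | 26% | 41% |

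For example, 0.05 / (0.26 × 0.50) = 0.05 / 0.13 = 38%.

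Run the other way, with p_F = 0.26 × (1 − s·w), total rejection is:

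- s = 0.25: 3.6% at w = 0.1, rising to 6.0% at w = 0.5.
- s = 0.50: 3.9%, 5.1%, 7.2% and 15.0% at w = 0.1, 0.2, 0.3 and 0.5.
- s = 0.75: 32.4% at w = 0.5.

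**5. In event counts**

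The planned control rate gives 0.26 × 96 ≈ 25 events. Fisher's test gives p = 0.072 for 25 against 14 and p = 0.045 for 25 against 13. Starting from equal arms, it takes 12 fewer events in one arm to reach significance.

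**The case against.** The case for leaving this as a minor wording point has substance.

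- **The larger figures need marked one-sided conduct.** This stands. If half of escalations fall in the band, a 5 to 8 point shift means withholding 38% to 62% of them in one arm only. Modest bias barely moves the error rate.
- **The direction is assumed.** This stands too. Nothing in the documents shows that staff favour furosemide, and handling could equally run the other way and hide a real effect. The illustration covers one direction only.
- **Both arms share the starting labetalol dose, the target, the dose ladder, the four-hourly schedule and automated cuffs.** These protect the readings. They do not fix when a reading in the band leads to a dose step.
- **The cited guideline may supply the rule.** It is cited for the titration target and was not available for this review. The claim is therefore only that these documents do not state the rule.
- **The documents do not say who decides on a step.** That clinicians do so is an inference, though a fair one.
- **The supportive analysis is extra work for a low-cost study.** In part. The SAP's daily means already draw on the in-hospital readings up to Day 2. What is added is later readings and the times of dose changes.

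**Conclusion.** The concern holds, and the plan should be changed. Following it as written leaves the primary comparison open to arm-dependent handling in the 150/100 to 160/110 band, and the planned analyses could not settle whether that occurred. This is more than missing wording, because the undefined judgement is itself the primary event.

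The size is unknown. Under no drug effect, a 26% control rate and 96 per arm, a 3-point handling shift takes total rejection from 3.5% to about 6%, 5 points to about 10%, and 8 points to about 22%. Nearly all of that is false benefit. How plausible each shift is depends on the share of escalations falling in the band, which the documents do not give. Confidence in the importance of the point is medium. The 96 per group stands.

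**What to change.** 1. **Protocol, Methods.** State one trigger for each labetalol step, identical in both arms. An example is two consecutive four-hourly readings with systolic at least 150 or diastolic at least 100; the investigators should choose the numbers. Replace 'and/or' with 'or' if that is what is meant. Keep the confirmed rule above 160/110 as the acute rule, and say that the escalation it requires is a labetalol step. A fixed trigger limits the influence of knowing the arm without needing a placebo.
2. **Data collection.** Record the sequential in-hospital readings and the time of each dose change.
3. **SAP.** Keep the primary test. Add a supportive Fisher's exact comparison, not key or co-primary, of the proportion of women whose post-randomisation readings meet either rule. Add a by-arm table of rule met against dose increased.

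**Cost.** A short protocol clarification and one SAP paragraph, with no extra patients or measurements. Sequential readings and dose-change times must be taken from charts, since the Protocol's variable list names neither. Clinicians lose a little discretion. The supportive endpoint is diluted when a woman is escalated before meeting the rule, since the dose increase may keep her from meeting it later; the by-arm table shows how many such women there are.

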Postpartum management of gestational hypertensive disorders using furosemide: A randomized controlled trial

Statistical Analysis Plan

Version Jan 9, 2020

[name]; [name], DO; [name]

The statistical analysis plan is based on the objectives of the study as follows:

Main Question: Does the use of furosemide plus labetalol improve blood pressures in the postpartum period of patients with gestational hypertensive disorders versus labetalol alone?

Primary:

Does the addition of a 5-day course of furosemide to labetalol avoid the escalation of anti-hypertensive therapy to control blood pressures.

Analysis plan: Randomization groups (labetalol + furosemide vs labetalol alone) will be compared using a Fisher's Exact test for number of patients who have had an escalation of labetalol dose at any time during their hospital stay.

Secondary:

Does the addition of furosemide to labetalol in postpartum hypertension:

1. Improve of systolic blood pressure, diastolic blood pressure and mean arterial pressure.

Analysis plan: Randomization groups will be compared on daily means for each outcome by repeated measures ANOVA to determine difference in outcomes across time (Day 0/Baseline, Day 1, and Day 2). One repeated measures ANOVA will be performed for each of the three outcomes (systolic blood pressure, diastolic blood pressure, and mean arterial pressure).

2. Shortened hospital stay

Analysis plan: Randomization groups will be compared on hospital length of stay using a Student T-test.

3. Affect breastfeeding status at 1 week postpartum visit in mothers planning to breastfeed.

Analysis plan: Randomization groups will be compared on breastfeeding status at the postpartum visit using a Fisher's Exact test.

4. Decrease readmission for postpartum hypertensive disorders.

Analysis plan: Randomization groups will be compared on the number of participants who were hospitalized after discharge using a Fisher's Exact test.

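### Highest SBP and DBP in the protocol (no time window) versus daily means over Days 0–2 in the SAP: one planned secondary outcome must be named

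*Protocol*

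**What the plan says.** Protocol, Objectives: the secondary objective is "Improve of systolic blood pressure, diastolic blood pressure and mean arterial pressure". It names no summary measure.

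Protocol, Methods, Outcome variables: the entries are "Highest systolic blood pressure (mmHg", "Highest diastolic blood pressure (mmHg" and "Mean arterial blood pressure". Only the first two are maxima. None has a time window, and no daily mean is listed.

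Protocol, Summary: "Student T-Test and Mann Whitney U tests will be utilized to compare continuous variables".

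Protocol, Methods, on measurement: "Measurement of blood pressure every four hours until patient discharge". A shorter stay is itself a secondary objective.

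SAP, Secondary 1: "Randomization groups will be compared on daily means for each outcome by repeated measures ANOVA", to look for a "difference in outcomes across time (Day 0/Baseline, Day 1, and Day 2". One such analysis is planned for each of SBP, DBP and MAP. The SAP does not mention a highest reading.

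**The concern.** A maximum and a daily mean are different quantities, and a treatment can move one without the other. The SAP does more than add detail to the protocol's SBP and DBP outcomes: it analyses another quantity by another method, and leaves the listed variables with no analysis of their own. Neither document says which version governs.

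The protocol describes no placebo or blinding, and says that the team running the study will analyse it. Two live definitions then allow a choice after the data are seen, on the question that both documents put first: whether furosemide improves blood pressure.

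The missing window adds a second, conditional problem. Readings run until discharge, so a maximum over the whole stay depends on how long the patient stays. The trial hopes that furosemide shortens the stay. If it does, part of any lower maximum in that arm could come from fewer readings.

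**Working it through.** **1. The documents side by side**

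| | Protocol | SAP |
|---|---|---|
| SBP, DBP | highest reading | daily mean |
| MAP | listed, no summary rule | daily mean |
| Window | none stated | Day 0/Baseline, Day 1, Day 2 |
| Test | t-test or Mann-Whitney (general rule for continuous variables) | repeated measures ANOVA |

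SBP and DBP conflict in measure and test. MAP differs in test, but its measure is only undefined in the protocol.

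**2. The plan's own figure**

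No power or sample size is given for any blood-pressure outcome. The only figure is 96 per group for the primary outcome (26% vs 8%, 90% power, two-sided 0.05). Exact enumeration of Fisher's test over the two binomials gives 89.95% power at 95 per group and 90.32% at 96, so the figure reproduces. It does not depend on this point, and 96 per arm is used below only as the trial size.

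**3. How a whole-stay maximum depends on the number of readings**

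From the protocol: one reading every 4 hours, so 24/4 = 6 a day, or 12, 18 and 24 readings over 2, 3 and 4 days. Assumed, because the documents give no values: within-patient SD 10 mmHg, independent readings, no trend.

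Expected excess of the maximum over the patient's mean = SD × E(max of k standard normals):

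- 2 days: 10 × 1.63 = 16.3 mmHg
- 3 days: 10 × 1.82 = 18.2 mmHg
- 4 days: 10 × 1.95 = 19.5 mmHg

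One extra day therefore adds 18.2 − 16.3 = 1.9 mmHg (3 vs 2 days) or 19.5 − 18.2 = 1.3 mmHg (4 vs 3 days), with no change in true pressure. Over within-patient SD 8–12 mmHg and correlation 0–0.8 between successive readings, the 3 vs 2 day difference is 1.5–2.8 mmHg.

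**4. What this does to a comparison of arms**

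Simulation with no true effect on pressure: 96 per arm, control stay averaging 3 days (SD 0.75), between- and within-patient SD 10 mmHg, correlation 0 or 0.5, t-test at 5%, 1,500 trials per scenario. Each cell shows the spurious difference favouring the shorter-stay arm, then the rejection rate.

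| Stay shorter by | Flat pressure | Falling 4 mmHg/day | Rising 3 mmHg/day |
|---|---|---|---|
| 0 days | about 0; 5% | about 0; 5% | about 0; 5% |
| 0.5 day | 1.0–1.1; 9–10% | 0.3; 5–6% | 1.9–2.0; 20–21% |
| 1 day | 2.2–2.4; 27–28% | 0.8–1.0; 8–9% | 4.1–4.2; 63–65% |

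The stays, SDs, correlations and trends are all assumptions. The direction is stable whenever stays differ; the size is not.

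**5. Whether daily means escape the problem**

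They do not grow with the number of readings. However, a patient discharged before Day 2 has no Day 2 mean, and the SAP has no missing-data rule. Repeated measures ANOVA run on complete cases would drop that patient.

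**The case against.** The strongest defence is that the SAP already fixes a measure, a test and days for all three pressures. It states that it is based on the study objectives, and those name no maximum, so it is consistent with them. On this view the conflict is confined to two lines of a variable list for a secondary outcome. This stands in part: the SAP narrows the choice, and the primary outcome is untouched. But the SAP does not say that it replaces the outcome list, and the highest readings remain listed outcomes that fall under the Summary's general test rule.

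A reader might infer that the protocol's SBP and DBP outcomes are biased by length of stay. The documents do not support that as a fact. The four-hourly schedule until discharge is a measurement schedule, not an outcome definition. A highest reading per day or over fixed days is equally open, and would largely avoid the problem. Even a whole-stay maximum is unbiased between arms if stays are equal. The documents give no expected stay, no expected difference in stay, and no SD or trend. Both arms receive labetalol titrated to a pressure target, so a flat course is doubtful, and a falling one makes the effect small.

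A reader might also infer that all three pressure outcomes are defined as maxima. MAP is not.

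**Conclusion.** The inconsistency is real for SBP and DBP: two different outcomes, with different tests, and nothing in either document to reconcile them. For MAP the protocol needs a definition. This should be corrected before the data are analysed, but it concerns a secondary outcome only.

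The length-of-stay effect is a conditional warning. It needs a maximum taken over the whole stay and a difference in stay between arms. Under the assumptions above, a stay 0.5 to 1 day shorter produces about 1.0–2.4 mmHg and 9–28% rejection with a flat course, less if pressure falls and more if it rises. No single figure in that range can be attributed to this trial.

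**What to change.** - Amend the protocol's outcome list so that the planned SBP, DBP and MAP secondary outcomes are the SAP's daily means on Days 0–2, and name the same test in both documents.
- Analyse them with a method that keeps patients discharged before Day 2, for example a mixed model for repeated measures using all available days, and state the missing-data assumption.
- If highest SBP and DBP are kept, define them per study day or over one common early window that nearly all patients complete. State how earlier discharge is handled, and label them descriptive. A 48-hour window would not be enough by itself, because inpatient readings stop at discharge for anyone who leaves sooner.

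The cost is wording in both documents and a little analysis work. The readings are already collected, and the primary outcome and the 96 per group do not change.
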